5.3 Lifestyle Considerations

5.3.1 Meals and Dietary Restrictions

The following restrictions apply:

Participants will be on a controlled diet during the hospitalized periods and accordingly before the start of study intervention cladribine/placebo until after the final dose

- Participants will refrain from consumption of Seville oranges, grapefruit or grapefruit juice and of any other drug metabolizing enzyme (e.g., CYP3A4 or other cytochrome P450 enzymes) inducing or inhibiting aliments, beverages or food supplements, e.g., broccoli, Brussels sprouts, star fruit, and products containing such fruit components (e.g., juices, marmalade, jam, etc.) from 2 weeks before the start of study intervention until after final dose.

5.3.2 Caffeine, Alcohol, and Tobacco

- During each dosing session, participants will abstain from ingesting caffeine- or xanthine-containing products (e.g., coffee, tea, cola drinks, and chocolate) for 12 hours before the start of dosing until after collection of the final pharmacokinetic (PK) and/or CCI sample
- During each dosing session, participants will abstain from alcohol for 24 hours before the start of dosing until after collection of the final PK and/or CCI sample
- Use of tobacco products will not be allowed from Screening until after the End of Study Visit beyond the limits specified in Exclusion Criterion #31. Exemption: In each period requiring PK blood sampling EE and LNG, participants are not allowed to consume tobacco products for 10 hours before the start of dosing on D14 until 4 hours postdose.

5.3.3 Activity

Participants will abstain from strenuous exercise for 24 hours before each blood collection for clinical laboratory tests. Participants may participate in light recreational activities (e.g., watching television or reading).

5.3.4 COVID-19 Vaccination Considerations

mRNA Vaccines:

No study drug interactions or specific consideration for the study population are so far known for mRNA vaccines. Therefore, there is no need to generally restrict the use of these vaccines prior, during, or after participating to the study.

In case that vaccination during the study may be considered, it should be scheduled either for the Run-in-Period or between Day 21 and Day 28 of study Periods 1 or 2, respectively, because vaccination during the treatment periods (between Days 1 to 20) shortly before cladribine/placebo administration may complicate causality assessment of AEs, and because there may be the possibility that cytokine release upon vaccination may increase the variability of the PK assessments after cladribine/placebo administration.

It is to be noted, that any vaccination during the study must be properly documented in the concomitant medication section of the eCRF.

Viral Vector Vaccines:

No study drug interactions are so far known for viral vector vaccines.

In contrast to the mRNA vaccines, since 01 April 2021, the use of viral vector vaccines for persons under 60 years of age is no longer recommended per CCI [REDACTED] as the risk of thrombosis is increased.

This guidance therefore also applies to the study population women aged 18 to 45 and should be adhered to, therefore no vaccination with a viral vector vaccine should be carried out during the study.

5.4 Screen Failures

Individuals who do not meet the criteria for participation in this study (screen failure) may be rescreened. Rescreened participants will be assigned a new participant number.

6 Study Intervention(s)

Study intervention is any investigational intervention(s), marketed product(s), placebo, or medical device(s) intended to be administered to a study participant per the study protocol.

6.1 Study Intervention(s) Administration

Study intervention administration details are provided in the table below.

Study Intervention Name:	Cladribine Tablets	Cladribine Placebo Tablets	Microgynon
Dose Formulation:	White, round, biconvex tablets of 8.5 mm diameter, engraved with 'C' on 1 side and '10' on the other side.	White, round, biconvex tablets of 8.5 mm diameter, engraved with 'C' on 1 side and '10' on the other side	Beige, sugar-coated tablets
Unit Dose Strength(s)/ Dosage Level(s):	10 mg / tablet	N/A (placebo)	Levonorgestrel (LNG) 150 µg and ethinyl estradiol (EE) 30 µg
Route of Administration:	Oral	Oral	Oral
Dosing Instructions:	Each treatment week consists of 5 consecutive days on which a participant receives 10 mg or 20 mg (one or 2 tablets) taken with water in the morning as a single daily dose, depending on body weight. For details, see Section 6.6	As for cladribine. For details, see Section 6.6	1 tablet daily for 21 days, starting on the first day of the menstrual cycle followed by 7 treatment-free days. Subsequent cycles (Study Periods 1 and 2): Tablet-taking from the next pack of Microgynon is continued after a 7-day treatment-free interval, beginning on the same day of the week as the Run-in-Period. For details, see Section 6.6
Supplier:	Merck KGaA	Merck KGaA	From commercially available sources; provided by Merck KGaA
Packaging and Labeling	Cladribine will be supplied in blister packages, containing 1, 4 and 6 tablets. Packages with 1 tablet for the study and the medical care treatment of the first year will be used. All IMPs will be packaged and labeled in accordance with all applicable regulatory requirements and Good Manufacturing Practice Guidelines.	Placebo will be supplied in blister packages, containing 1, 4 and 6 tablets. All IMPs will be packaged and labeled in accordance with all applicable regulatory requirements and Good Manufacturing Practice Guidelines.	Microgynon 21 will be supplied and packaged and labeled in accordance with all applicable regulatory requirements and Good Manufacturing Practice Guidelines.

EE=ethinyl estradiol; IMP=investigational medicinal product; LNG=levonorgestrel; N/A=not applicable; µg=microgram; mg= milligram; mm= millimeter

6.1.1 Medical Device(s) Use

Not applicable.

6.2 Study Intervention(s) Preparation, Handling, Storage, and Accountability

The Investigator, institution, or the head of the medical institution (where applicable) is responsible for study intervention accountability, reconciliation, and record maintenance (i.e., receipt, reconciliation, and final disposition records).

- Upon receipt of the study intervention(s), the Investigator or designee must confirm appropriate temperature conditions have been maintained during transit and any discrepancies are reported and resolved before use. Also, the responsible person will check for accurate delivery and acknowledge receipt by signing or initialing and dating the appropriate document and returning it to the location specified. A copy will be archived for the Investigator Site File.
- Only participants enrolled in the study may receive study intervention(s) and only authorized site staff may supply or administer it (where enrolled is defined as a participant who has started the Run-in-Period, see [Table 7](#)). All study intervention(s) must be stored in a secure, environmentally-controlled, and monitored (manual or automated) area, in accordance with the labeled storage conditions, and with access limited to the Investigator and authorized site staff.
- Dispensing will be recorded on the appropriate accountability forms so that accurate records will be available for verification at each monitoring visit.
- Study intervention(s) accountability records at the study site will include the following:
 - Confirmation of receipt, in good condition and in the defined temperature range
 - The inventory provided for the clinical study and prepared at the site
 - The dose(s) each participant used during the study
 - The disposition (including return, if applicable) of any unused study intervention(s)
 - Dates, quantities, batch numbers, container numbers, expiry dates, formulations for study interventions prepared at the site, and the participant numbers
- The Investigator site will maintain records, which adequately documents that participants were provided the doses specified in this protocol, and all study intervention(s) provided were fully reconciled
- Unused study intervention(s) must not be discarded or used for any purpose other than the present study. No study intervention that is dispensed to a participant may be re-dispensed to a different participant
- A Study Monitor will periodically collect the study intervention(s) accountability forms and check all returns (both unused and used containers) before authorizing their destruction by the study site or arranging for their return to the Sponsor or designee. In the event the site is unable to destroy unused and used containers, it is recommended local or regional destruction is organized by the CRO. Unused and used containers must only be returned to the Sponsor CMO depot, if required by the local law
- Further guidance and information for the final disposition of unused study interventions are provided in the Operations Manual.

6.3 Measures to Minimize Bias: Study Intervention Assignment and Blinding

6.3.1 Study Intervention Assignment

Participants will be randomized in a 1:1 ratio to 1 of the 2 sequences of the crossover design.

On Day 21 of the Run-in-Period, participants will be assigned a unique number (randomization number) in ascending numerical order at each study site. The randomization number encodes the participant's assignment to 1 of the 2 sequences of the study, per the randomization schedule generated prior to the study by the Clinical Trial Supply Department (CTS) Department at PPD .

6.3.2 Blinding

Blinding Method

To blind cladribine treatment, matched placebo tablets will be used. Microgynon tablets will be administered open-label.

Assignment Method Retention

Unblinding may be done utilizing blind-break envelopes provided to each site. All breaks of the study blind must be adequately documented.

Unblinding Clinical Studies for Sample Analysis of Special Data

Not applicable.

Unblinding Process After End of Study for Each Participant

Each participant assigned to the placebo-cladribine sequence will receive the second weekly dose of cladribine after the End of Study Visit as part of standard medical care (see also Section 4.1). Therefore, after the End of Study Visit of each participant, the Investigator will be unblinded for that participant, according to the timelines and procedures specified in the following:

After data entry of Day 21 of Study Period 2 in the electronic Case Report Form (eCRF), a trigger email is initiated to the PPD Project Manager (PM) and the Clinical Research Associate announcing the date of the End of Study Visit for the participant. At the End of Study Visit, in the eCRF a confirmation form is completed by the Investigator that all data have been entered. Subsequently, a second trigger email is initiated confirming the End of Study Visit for the participant has been completed. Thereafter, the PPD PM is requesting unblinding for the participant's study intervention at the PPD CTS Department. Information on unblinded treatment assignment is transferred from PPD CTS to the site via PM and Clinical Research Associate. This information is forwarded to the designated IMP distribution site responsible for delivering cladribine tablets for the second cladribine 5-day treatment.

For further information on study intervention after the end of the study, see Section 6.7.

6.3.3 Emergency Unblinding

In an emergency, the Investigator is solely responsible for determining if unblinding of a participant's study intervention assignment is warranted. Participant safety must always be the first consideration in this decision. If the Investigator decides that unblinding is warranted, the Investigator should make every effort to contact the Sponsor prior to the unblinding, unless this could delay emergency treatment. The Sponsor must be notified within 24 hours after unblinding. The Investigator must provide the Sponsor the reason for unblinding without revealing the study intervention, except to the designated drug safety representative via the Emergency Unblinding Notification Form. The date of and reason for unblinding must be recorded in the source documents. Contact information for unblinding in an emergency is given on the participant emergency card provided to each participant, as noted in [Appendix 2](#) (Study Governance Considerations).

The Sponsor's Global Patient Safety department will submit any Suspected Unexpected Serious Adverse Reactions (SUSAR) reports to regulatory authorities and ethics committees with unblinded information, per applicable regulations. Only blinded information will be provided to the study team.

Under certain circumstances, Global Patient Safety may be required to unblind the treatment assignment for an individual participant following a serious adverse event (SAE) or other serious event; for example, if an expedited regulatory report is required. See Section 8.3.4 for further details on expedited reporting and SAEs.

Unblinding of the period assignment of an individual participant due to emergency will not per se render this participant unevaluable for PK and [REDACTED] assessments, provided the unblinding or related emergency procedure will not alter the planned per-protocol study interventions (see Section 9.3).

6.4 Study Intervention Compliance

During the 2 cladribine treatment periods, while participants are hospitalized, administrations of cladribine tablets will be performed by dedicated site staff in accordance with the protocol requirements and specifications of the Investigator. This includes checking the oral and buccal cavity with the aid of a flashlight and tongue depressor. The proper administration of the study medication will be documented on the individual eCRF.

Participants will be provided with a pack of Microgynon for 1 cycle during the Screening Visit and a diary for recording daily Microgynon intake. The diary entries are checked for compliance of Microgynon intake during ambulatory visits on Day 7, 14 and 21 of the first cycle (Run-in-Period). On Day 21 of the first cycle (Run-in-Period) and Day 21 of Study Period 1, participant diary and empty Microgynon packing is collected, and a new diary and Microgynon pack is delivered. Additionally, therapeutic drug monitoring (PK sampling for EE and LNG) is performed on Days 7, 14 and 21 of the first cycle (Run-in-Period), and on Days 13, 14 and 15 of each period.

Participants must be 100% compliant to cladribine and placebo intake to be eligible for Pharmacokinetic and [REDACTED] evaluation (see Populations for Analysis, Section 9.3).

Assessment of compliance with respect to Microgynon intake will be based on participant reports (diary) and pill counts during the study, and at the end of the study on retrospective analysis of EE/LNG blood levels of all samples collected. Deviations from compliance to Microgynon for each of the 21 days of intake per cycle, if any, will be judged by the Investigator whether such protocol non-compliance is considered significant. In case of significant non-compliance, the participant would be withdrawn from further therapy or the study (see Section 7.1 and 7.2).

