1.3 Schedule of Activities

- The Schedule of Activities (SoA) is provided below.

Schedule of Activities – Screening, Run-in-Period and Study Period 1

Assessments & Procedures	Screening (up to 21 days before Day 1) ^b	Run-in- Period	Intervention Study Period 1 (Days)									Notes	
			D 1 to 28	D 8	D 9	D 10	D 11	D 12	D 13	D 14	D 15		D 21
Residency				X	X	X	X	X	X	X	X		In individual cases Investigator may allow participants to stay overnight at home from Day 8 to Day 12. In-patient stay is required from the evening of Day 13 until discharge on Day 15 after completion of all planned study assessments.
Ambulatory Visit	X	X										X	Run-in-Period: ambulatory visits on Days 7, 14 and 21
Written Informed Consent	X												Prior to any screening procedures
Inclusion and Exclusion Criteria review	X			X ^a									a Re-check before administration on: contraception method, blood loss and lifestyle considerations. Results of safety laboratory on Day 21 of Run-in-Period (Baseline).
Demographic Data	X												
Physical Examination	X												
Herpes Zoster Serology	X												Serology diagnosis, if ABS negative vaccination and at least 4 weeks before cladribine administration
Medical History / Concomitant Disease	X												
Prior and Concomitant Treatment	X	X	X	X	X	X	X	X	X	X	X	X	

Assessments & Procedures (cont'd, Study Period 1)	Screening (up to 21 days before Day 1) ^b	Run-in- Period D 1 to 28	Intervention Study Period 1 (Days)									Notes
			D 8	D 9	D 10	D 11	D 12	D 13	D 14	D 15	D 21	
Hematology, Clinical Chemistry & Urine Analysis	X	X								X		Run-in-Period on Day 21 (Baseline)
QuantiFERON®-TB Test	X											Done in local laboratory
Serum Pregnancy Test	X											
Urine Pregnancy Test		X	X									A negative urine pregnancy test must be in place at Day 7 of Run-in-Period and on Day 8 of Study Period 1.
Alcohol Breath Test / Drugs of Abuse	X		X									See Appendix 5 . On Day 8 urine drug screen is done locally
Height / Weight / Body Mass Index (BMI)	X	X									X	Additional weight control: Run-in-Period on Day 21 and on Day 21 Study Period 1
Vital Signs	X	X		X	X	X	X	X	X			Run-in-Period on Days 7, 14 and 21. Days 9-13 predose and 1 h postdose; on Day 14 at 24 h and 25.5 h postdose (Day 13) of cladribine/placebo administration
12-lead ECG	X			X						X		On Day 9 predose and 1.5 h postdose; on Day 14 at 24 h and 25.5 h postdose (Day 13) of cladribine/placebo administration
Randomization		X										Within 10 days after Run-in-Period Day 21

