Participants who withdraw from the study for any reason or do not have a full PK dataset will not routinely be replaced. If the assumed drop-out rate of 18 % to 30% will be unexpectedly higher, a discussion should occur between the Investigator and the Sponsor regarding whether a replacement may be considered. The number of participants evaluable for BE (16 participants) need to be maintained. Each replacer will be assigned to the treatment sequence of the replaced participant. Details on this procedure are described in the Operations Manual.

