9.4.4 Analysis of Primary Endpoints

The PK evaluation will be based upon the PK Analysis Set. The statistical analysis of primary PK parameters $AUC_{\tau,ss}$ and $C_{max,ss}$ of EE and LNG (the active ingredients of the Microgynon treatment) will be performed using an analysis of variance (ANOVA) model including TREATMENT, PERIOD, SEQUENCE and SUBJECT (SEQUENCE) as fixed effects. Parameters will be log-transformed before they are processed. LSMEANS for Test – Reference differences will be estimated for all 4 primary endpoints together with 90% confidence intervals, resulting in Test/Reference ratios and corresponding 90% confidence intervals following back-transformation.

Bioequivalence (which means absence of drug-drug interaction) will be concluded, if all 4 90% CIs for the TEST/REFERENCE ratios are fully contained within the [0.8000 to 1.2500] acceptance range.

[REDACTED]

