Study Administrative Structure

This clinical study will be sponsored by Merck KGaA, [name].

Cladribine will be administered in the present study as per its approved posology, therefore no Safety Monitoring Committee is foreseen.

The study will be conducted in European countries in University hospitals and Centers / Clinics of Neurology. The PK-part of the study requires hospitalization from Days 8 to 15 of Study Periods 1 and 2. In case specialized Centers/Clinics of Neurology do not have the structure and capability to allow hospitalizations and extensive PK sampling / sample handling, the Days 8 to 15 of Study Period 1 and 2 will be conducted in another study site (herein referred to as “PK site”; e.g., in Germany the [REDACTED] in [REDACTED] a dedicated Phase 1 unit). The specialized Centers/Clinics of Neurology which are only responsible for participant recruitment, ambulatory visits, and referral to the PK sites are herein referred to as “Investigational sites”. There may be up to 6 Investigational sites collaborating with one PK site.

In this case the PI responsibilities of “Investigational site” and “PK site” within the study are as follows:

Investigational site (see also [Section 1.3](#) “Schedule of Activities”):

- Main study contact for Screening and Run-in-Period, until Day 7 and after hospitalization discharge at Day 15 of each study period and End of Study
- Informing and Obtaining of Informed Consent for the entire study
- Screening Activities
- Assessment of Inclusion/Exclusion criteria
- Microgynon: delivery, return, compliance and drug accountability activities
- Cladribine/Placebo: delivery and compliance activities on Days 16-19, collection of empty blisters for transfer to PK site
- Run-in-Period-activities on Days 7, 14 and 21
- Request randomization on Day 21 of Run-in-Period at CTS Department at [REDACTED] GmbH
- Ambulatory visit activities on Day 21 of each study period and End of Study
- Recording of adverse events and prior/concomitant medication.

PK site (see also [Section 1.3](#) “Schedule of Activities”):

- Main study contact on Days 8-15 of Study Periods 1 and 2
- Intervention period Days 8 – 15 activities incl. PK [REDACTED] sampling
- Recheck of relevant inclusion/exclusion criteria on Day 8 in Study Period 1
- Recording of adverse events and concomitant medication on Days 8-15 of Study Periods 1 and 2

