- Cladribine: delivery, return, compliance and drug accountability activities of Study Periods 1 and 2

(Cladribine packages for Days 16-19 will be forwarded from Investigational site to PK site after Day 21)

Communication between Investigational site and PK site:

After completed screening and enrolment of a new subject the Investigational site will forward a copy of the signed ICF per e-Mail / Fax to the corresponding PK site (if applicable).

The [REDACTED] will inform the corresponding PK site by email when a Cladribine/Placebo shipment and randomization request has been received from an Investigational site.

On Day 21 of the Run-in-Period the PK site will inform the corresponding investigational site of the successful randomization of the patient per e-Mail / Fax. On Day 15 of the Study Periods 1 and 2 the PK site will inform the corresponding investigational site of the successful discharge of the patient per e-Mail / Fax.

A contact list of the PK site study team will be filled in the Investigator Site File of the Investigational sites. The contact lists of the Investigational sites will be filed in the Investigator site file of the PK study site.

In case of clarification or emergency with regards to a participant of the study the Investigators / study team of the corresponding sites will get in touch as needed.

Capture of Source Data and CRF data:

Safety blood sampling, Adverse Event/SAE, concomitant medication and any other safety reporting are the responsibility of the Investigational site with exception of Days 8-15 of Study Periods 1 and 2 where these responsibilities pass over to the PK site.

Investigational and PK sites are entering subject data in the same eCRF therefore both sites are aware of the current participant situation. Safety-relevant data must have been completely entered into the eCRF at the days when a patient is referred from an Investigational site to a PK site and vice versa.

Safety lab reports from the Central lab will be sent to the PK site and the corresponding Investigational site in parallel.

All sites may engage so called “referral sites” (e.g. Neurology Outpatient Practices). Referral sites refer patients to Investigational sites for potential inclusion into the study.

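### Staff-observed dosing is written for cladribine/placebo but not for the in-house Microgynon tablets behind all four primary endpoints; the likely cost is precision and interpretability, not a false interaction

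*Protocol*

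**What the plan says.** Protocol 6.4 states that, during hospitalization, "administrations of cladribine tablets will be performed by dedicated site staff in accordance with the protocol requirements", with inspection of the mouth. Section 6.6.2 extends the same handling to placebo. On the contraceptive, 6.4 says "Assessment of compliance with respect to Microgynon intake will be based on participant reports (diary) and pill counts during the study". The sentence then adds a retrospective review of measured EE and LNG concentrations at the end of the study, and the section schedules EE/LNG monitoring on Days 13, 14 and 15 of each period.

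Where recruiting and PK sites are separate, Appendix 2 lists "Microgynon: delivery, return, compliance and drug accountability activities" under the Investigational site. The PK site, the main contact for Days 8-15, has "Cladribine: delivery, return, compliance and drug accountability activities of Study Periods 1 and 2".

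The Schedule of Activities adds: "In individual cases Investigator may allow participants to stay overnight at home from Day 8 to Day 12". In-patient stay is compulsory from the evening of Day 13. Section 6.6.3 places the Microgynon tablet one hour before cladribine/placebo.

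AUCtau,ss and Cmax,ss of EE and LNG come from the Day 14 profile. Under 9.4.4, "LSMEANS for Test – Reference differences will be estimated for all 4 primary endpoints together with 90% confidence intervals", and all four intervals must lie inside the equivalence limits. The PK Analysis Set in SAP 8.2 requires full cladribine/placebo compliance, but treats Microgynon non-compliance as a matter of judgement.

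**The concern.** The study measures the contraceptive, so the Microgynon tablet is the input to every primary endpoint. Its intake is nevertheless verified less strictly than that of the drug whose effect is being tested. The diary is self-reported, and a pack count cannot date a missed tablet. Diary and packs also come back on Day 21 of Study Period 1 and at the End of Study Visit for Period 2, after the Day 14 profiles.

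That leaves the EE/LNG levels as the only objective check, and they are also the outcome. Protocol 2.2 says the study exists because the in vitro data on CYP3A4 induction were inconclusive. Induction lowers EE and LNG, and so does a missed tablet. If a low profile is excluded as non-compliance, real induction may be removed. If it is kept, a missed tablet stays in the data as noise. Observed intake would settle the question independently of the outcome.

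**Working it through.** **Inputs.** From the documents: 90% intervals that "are fully contained within the [0.8000 to 1.2500] acceptance range" (9.4.4), and "The number of participants evaluable for BE (16 participants) need to be maintained" (7.2). The 16 cannot be reproduced, because no variability, power or assumed ratio is visible. Assumed: half-life 8-36 h, one-compartment linear kinetics at steady state with rapid absorption, and within-subject CV of 15%, 20% or 25%. The calculation covers AUCtau; the effect on Cmax was not computed.

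**One participant.** Let e = 2^(-24/half-life). A tablet taken k days before Day 14 supplies the share e^k × (1 - e) of Day 14 AUCtau. If it is missed, that share is lost:

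| Half-life | Day 14 | Day 13 | Day 12 | Day 11 | Day 10 | Day 9 |
|---|---|---|---|---|---|---|
| 8 h | 87.5% | 10.9% | 1.4% | 0.2% | <0.1% | <0.1% |
| 12 h | 75.0% | 18.8% | 4.7% | 1.2% | 0.3% | 0.1% |
| 24 h | 50.0% | 25.0% | 12.5% | 6.3% | 3.1% | 1.6% |
| 36 h | 37.0% | 23.3% | 14.7% | 9.3% | 5.8% | 3.7% |

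Two of these columns have a ceiling whatever the half-life. For k = 1 the share peaks at e = 1/2, giving 25%. For k = 2 it peaks at e = 2/3, giving 4/27 = 14.8%.

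**What the samples would show.**

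- *Day 14 missed:* no absorption peak in the nine-sample profile.
- *Day 13 missed:* the Day 14 predose level falls by 1 - e, which is 37-88% over this range, while the Day 13 predose level is unchanged.
- *Day 12 missed:* the Day 13 predose level falls by 1 - e, but the Day 14 predose level by only e(1 - e), 11-25%. That is a trace, but there is no earlier sample in the period to compare it with.
- *Day 11 missed:* the Day 13 predose level falls by 11-25%.
- *Day 10 missed:* the Day 13 predose level falls by e²(1 - e), 1-15%.

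Detection therefore weakens going back from Day 12, as does the effect on AUCtau.

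**The trial mean.** If m of 16 participants lose a fraction L in the cladribine period, the geometric mean ratio becomes (1 - L)^(m/16).

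- L = 15%, m = 1: 0.85^(1/16) = 0.990.
- L = 25%, m = 1: 0.75^(1/16) = 0.982. With m = 2: 0.965.
- To reach 0.80 with L = 25%: m = 16 × ln 0.80 / ln 0.75 = 12.4 participants, all in the cladribine period.

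**Chance of passing one endpoint.** These are 100,000 simulated crossovers with 16 participants, 14 degrees of freedom and a true ratio of 1.00. One participant loses 25% in the cladribine period:

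| CV | No miss | One 25% loss |
|---|---|---|
| 15% | 98.2% | 96.9% |
| 20% | 83.4% | 80.2% |
| 25% | 57.3% | 54.4% |

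If the affected period is random, the mean ratio stays at 1.00 and the pass rates are nearly the same (96.9%, 80.2%, 54.2%). The cost comes through the width of the interval.

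**The case against.** The case against is substantial.

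- Verification does not rest on diary and pill count alone, as a reader who stopped halfway through the 6.4 sentence might infer. Blood levels are the third layer.
- The tablets with most influence are tied to the site. On Days 13 and 14 an EE/LNG sample is due in the hour before Microgynon, and SAP 8.1 makes a predose sample taken after dosing a protocol deviation. Taking the Day 13 tablet at home would break the sampling schedule, so the 25% figure does not describe compliant home dosing.
- Appendix 2 gives the PK site the Day 8-15 activities in the Schedule of Activities, which include Microgynon administration. Protocol 6.2 restricts supply and administration to authorized staff. SAP 13 lists the date and time of every drug administration.
- Non-compliance judged significant leads to withdrawal. Home nights are for individual cases with written instructions, and the two-site arrangement applies only at some sites.

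Most of this stands, and it limits the size of the problem. It does not close the gap. None of these provisions requires anyone to witness the tablet, none names a Microgynon compliance duty at the PK site, and no rule says which EE/LNG pattern counts as a miss.

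**Conclusion.** The gap is real and small. In-house Microgynon intake has no specified observation, and the objective check that remains uses the outcome itself. The exposed tablets are mainly those of Days 9-12. A missed Day 12 tablet costs that participant about 1-15% of Day 14 AUCtau, and earlier ones cost less.

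A reader might infer that one missed tablet could mimic an interaction, since a Day 13 miss can bring an individual ratio to 0.75. The documents do not support that. The 0.80-1.25 limits apply to the interval for the mean ratio, which one such participant in 16 moves only to about 0.98. Because cladribine/placebo is blinded and randomized by sequence, a miss has no expected direction. The main cost is a wider interval, with about 1 to 3 percentage points off the chance of passing one endpoint for a 25% loss in one participant, and an ambiguous low profile. A 50% loss in one participant would cost more (83.4% to 64.2% at a CV of 20%). In this model a loss of that size from one tablet means the Day 14 tablet, whose absence the profile would show.

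The half-life and CV ranges are assumptions.

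**What to change.** In Protocol 6.4, state that Microgynon on Days 9-14 of both periods is taken at the site under staff observation, with the clock time entered in the eCRF, including on mornings after a night at home. In Appendix 2, assign Microgynon administration and compliance on Days 8-15 to the PK site. Keep the diary and pill count for ambulatory days.

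This is a change of wording and changes no planned figure. Staff already see each participant on those mornings, for cladribine/placebo on Days 9-13 and for PK sampling on Day 14. The downside is that women sleeping at home must arrive about one hour earlier.
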